Title	Assessment of Myocardial Ischemic-Reperfusion Injury During Off- and On- Pump CABG (AMIRI-CABG) ClinicalTrials.gov Identifier: NCT03050489	
Authors *	[name]	
Trial design	Prospective non-randomized single center	
Methods		
Participants	Eligibility criteria: multivessel coronary artery disease with indications for elective coronary artery bypass grafting	
Interventions	Group 1: off-pump CABG Group 2: on-pump CABG Group 3: pump-assisted CABG (on-pump CABG without aortic cross-clamping)	
Objective	To compare level of MPO between three groups of intervention	
Primary objective	To compare ischemic-reperfusion injury between three groups of intervention	

Assessment of Myocardial Ischemic-Reperfusion Injury During Off- and On- Pump CABG  
 (ClinicalTrials.gov Identifier: NCT03050489). Corresponding author: [name]  
[[contact]](mailto:[contact]) [contact]

Date of the document 06 December 2016

Secondary objective	To assess ability of MPO to predict worse outcome (death) To assess relation between MPO and TnI	
Outcome	MPO level after CABG, death after CABG	
Randomization	Non-randomized allocation. Heart Team decision.	
Blinding (masking)	None	
Results		
Numbers randomized	Number of participants screened n=500  Allocated (non-randomized): off-pump CABG (n=181), on-pump CABG (n=128), pump-assisted CABG (n=27)	
Recruitment	Complete	
Numbers analyzed	Off-pump CABG: 181 On-pump CABG: 128 Pump-assisted CABG: 27	
Outcome	Could MPO predict death during 30 days after CABG	
Harms	Important adverse events or side effects	
Conclusions	CPB activates leucocytes that cause myocardial damage  Preoperative MPO level could evaluated as a predictor of myocardial damage and worse outcome after CABG	
Trial registration	ClinicalTrials.gov Identifier: NCT03050489	
Funding	Assessment of regenerative ability after cardiac surgery	

*Table 2 Statistical analysis synopsis*

Assessment of Myocardial Ischemic-Reperfusion Injury During Off- and On- Pump CABG ClinicalTrials.gov Identifier: NCT03050489	
Hypothesis	Ischemic – reperfusion injury are comparable between groups
Primary objective	To compare ischemic-reperfusion injury during off-pump, on-pump and pump – assisted CABG
Secondary objective	To assess ability of myeloperoxidase to predict worse outcome after CABG

Assessment of Myocardial Ischemic-Reperfusion Injury During Off- and On- Pump CABG  
 (ClinicalTrials.gov Identifier: NCT03050489). Corresponding author: [name]  

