#### Ischemic – reperfusion injury analysis (TnI level 1st day after CABG)

Hypothesis: TnI level 1st after CABG depends on length of operation, length of cardiopulmonary bypass, MPO level before procedure and just after suture performing

Method of hypothesis testing: ANCOVA

ANCOVA model:  $LGTnI1 = LGMPOPostOp LGMPOPreOp CPBTYPE LGMPOPreOp*CPBTYPE AoClamp CPBTime AoClamp*CPBTime OpTime CPBTime* OpTime AoClamp*OpTime$

*Table 11 Variables descriptions*

Variable	Description	Note
TnI1	Troponin I level 1 st day after procedure	Continuous variable
LGMPOPostOp	Logarithm of MPO level during CABG (after suture performing)	Log – transformation for normal distribution
LGMPOPreOp	Logarithm of MPO level before CABG (after suture performing)	Log – transformation for normal distribution
CPBTYPE	Group of intervention	1 – off-pump CABG 2 – on – pump CABG 3 – pump-assisted CABG
AoClamp	Length of aortic cross-clamping, min	Continuous variable
CPBTime	Length of cardiopulmonary bypass, min	Continuous variable
OpTime	Length of procedure, min	Continuous variable
*	Interaction effect	

*Table 12 Characteristics of model*

Source	Sum of Squares	df	Mean Square	F	p	Eta Square

Assessment of Myocardial Ischemic-Reperfusion Injury During Off- and On- Pump CABG (ClinicalTrials.gov Identifier: NCT03050489). Corresponding author: [name] [[contact]](mailto:[contact]) [contact]

Date of the document 06 December 2016

Model	249.3	14	17.8	10.4	0.0001	0.44
-------	-------	----	------	------	--------	------

*Table 13 General linear model characteristics*  $LGTnI1 = LGMPOPostOp LGMPOPreOp CPBTYPE$   
 $LGMPOPreOp*CPBTYPE AoClamp CPBTime AoClamp*CPBTime OpTime CPBTime* OpTime$   
 $AoClamp*OpTime$

Source	Sum of Squares (Type III)	df	Mean Square	F	p	Partial Eta Squared
LGMPOPostOp	2.0	1	2.6	1.2	0.3	0.006
LGMPOPreOp	0.8	1	0.8	0.5	0.5	0.002
AoClamp	2.3	1	2.3	1.4	0.2	0.007
CPBTime	2.2	1	2.2	1.3	0.3	0.007
OpTime	23.3	1	23.3	13.6	0.0003	0.07
CPBType	3.9	2	1.9	1.1	0.3	0.01
CPBTime*OpTime	0.7	1	0.7	0.4	0.5	0.002
AoClamp*CPBTime	0.4	1	0.4	0.22	0.6	0.001
AoClamp*OpTime	3.5	1	3.5	2.1	0.2	0.01
LGMPOPostOp*CPBTYPE	4.1	2	2.1	1.2	0.3	0.01
LGMPOPreOp*CPBTYPE	0.4	2	0.2	0.1	0.9	0.001

**Summary:** troponin I level 1st day postoperatively depends on length of operation

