#### Ischemic – reperfusion injury analysis (TnI level 1st day after on – pump CABG)

Hypothesis: TnI level 1st day after on-pump CABG depends on length of operation, length of cardiopulmonary bypass, MPO level before procedure and after suture performing

Method of hypothesis testing: ANCOVA

ANCOVA model:  $LGTnI1 = LGMPOPostOp LGMPOPreOp CPBTYPE LGMPOPreOp*CPBTYPE$   
 $AoClamp CPBTime AoClamp*CPBTime OpTime CPBTime* OpTime AoClamp*OpTime$

*Table 14 Variables description*

Variable	Description	Note
TnI1	Troponin I level 1 st day after procedure	Continuous variable
LGMPOPostOp	Logarithm of MPO level during CABG (after suture performing)	Log – transformation for normal distribution
LGMPOPreOp	Logarithm of MPO level before CABG (after suture performing)	Log – transformation for normal distribution
CPBTYPE	Group of intervention	1 – off-pump CABG 2 – on – pump CABG 3 – pump-assisted CABG
AoClamp	Length of aortic cross-clamping, min	Continuous variable
CPBTime	Length of cardiopulmonary bypass, min	Continuous variable
OpTime	Length of procedure, min	Continuous variable
*	Interaction effect	

Assessment of Myocardial Ischemic-Reperfusion Injury During Off- and On- Pump CABG (ClinicalTrials.gov Identifier: NCT03050489). Corresponding author: [name] [[contact]](mailto:[contact]) [contact]

Date of the document 06 December 2016

*Table 15 Characteristics of model*

Source	Sum of Squares	df	Mean Square	F	p	Eta Square
Model	39.7	8	4.96	5.4	0.0001	0.4

*Table 16 Characteristics of model LGTnI1 = LGMPOPostOp LGMPOPreOp CPBTYPE*

*LGMPOPreOp\*CPBTYPE AoClamp CPBTime AoClamp\*CPBTime OpTime CPBTime\* OpTime AoClamp\*OpTime*

Source	Sum of Squares (Type III)	df	Mean Square	F	p	Partial Eta Squared
LGMPOPostOp	1.3	1	1.3	1.4	0.2	0.02
LGMPOPreOp	3.9	1	3.9	4.2	0.04	0.06
AoClamp	0.9	1	0.9	1.0	0.3	0.02
CPBTime	7.4	1	7.4	8.1	0.006	0.1
OpTime	3.4	1	3.4	3.7	0.06	0.05
CPBTime*OpTime	0.01	1	0.1	0.1	0.8	0.0009
AoClamp*CPBTime	5.5	1	5.5	5.9	0.02	0.08
AoClamp*OpTime	1.6	1	1.6	1.7	0.2	0.026

**Summary:** troponin I level 1st day after on-pump CABG affected by length of cardiopulmonary bypass, preoperative MPO level and interaction of duration of aortic cross clamping and length of cardiopulmonary bypass.

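### The on-pump Summary states as an effect of pre-operative MPO on day-1 troponin what is one p=0.04, the only one of eight printed MPO–troponin tests below 0.05, with no multiplicity adjustment stated

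*Combined protocol and SAP*

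**What the plan says.** The combined protocol and SAP fits an ANCOVA for log day-1 TnI in all patients (Tables 12 and 13), then separately for on-pump (Tables 15 and 16), off-pump (Tables 18 and 19) and pump-assisted CABG (Table 21). Each section closes with a Summary.

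- **On-pump.** Day-1 TnI is said to be "affected by length of cardiopulmonary bypass, preoperative MPO level and interaction of duration of aortic cross clamping and length of cardiopulmonary bypass". The row behind the MPO part, in Table 16, is "LGMPOPreOp 3.9 1 3.9 4.2 0.04 0.06". Post-operative MPO in the same table is "LGMPOPostOp 1.3 1 1.3 1.4 0.2 0.02".
- **All patients.** Table 13 gives pre-operative MPO as "LGMPOPreOp 0.8 1 0.8 0.5 0.5 0.002" and its interaction with technique as "LGMPOPreOp*CPBTYPE 0.4 2 0.2 0.1 0.9 0.001". The Summary there names only length of operation.
- **Off-pump.** Table 19 gives p=0.1 for pre-operative and p=0.8 for post-operative MPO. The Summary, which as printed refers to on-pump CABG, names only length of operation.
- **Pump-assisted.** Only the overall model is printed (F=0.8, p=0.6). The Summary reports no dependence on MPO.

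The Conclusions row of Table 1 reads: "Preoperative MPO level could evaluated as a predictor of myocardial damage and worse outcome after CABG". Adjustment for multiple comparisons is mentioned for the group comparisons under Baseline Characteristics, Primary endpoint analysis and Secondary Endpoint Analysis, but not for any ANCOVA term. No significance level is stated. Table 2 and the Sample Size Justification call the study exploratory.

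**The concern.** The on-pump Summary uses causal, unqualified wording for a result just under 0.05 in one of several models, each of which tests both pre- and post-operative MPO. Some such result is likely by chance alone, and a reader cannot tell from the Summary that it was one of many.

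Printed one after another, the technique summaries also invite the reading that pre-operative MPO matters on-pump and not elsewhere. One p-value below 0.05 and others above it is not a test of that difference.

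What is at stake is the Table 1 conclusion. The Table 16 row is the only printed MPO–TnI result below 0.05. The death model (Tables 22 and 23) uses post-operative MPO, so it does not support a statement about pre-operative MPO. The primary endpoint comparison of MPO after operation is not affected.

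**Working it through.** **1. Reproducing the printed p-values.** The error df are not printed. They follow from each overall model line as F × df_model × (1 − η²)/η², and the error mean square is MS_model/F.

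- On-pump, Table 15, "Model 39.7 8 4.96 5.4 0.0001 0.4": error df = 5.4 × 8 × 0.6/0.4 = 64.8, about 65 (52 to 81 allowing for rounding), so about 65 + 8 + 1 = 74 of the 128 patients. Error mean square = 4.96/5.4 = 0.919, and 3.9/0.919 = 4.25 against the printed F of 4.2. F=4.2 on (1, 65) df gives p = 0.044 (0.042 to 0.047). The printed 0.04 is confirmed.
- All patients, Table 12: error df = 10.4 × 14 × 0.56/0.44, about 185; error mean square = 17.8/10.4 = 1.71. For the interaction of pre-operative MPO with technique, 0.2/1.71 = 0.117 on (2, 185) df gives p = 0.89; the printed F of 0.1 gives 0.905. The printed 0.9 is confirmed. Pre-operative MPO, F=0.5, gives p = 0.48 (printed 0.5).
- Off-pump, Table 18: error df = 7.0 × 3 × 0.85/0.15 = 119. F=2.36 gives p = 0.127 (printed 0.1).
- Pump-assisted, Table 21: error df = 0.8 × 4 × 0.55/0.45 = 3.9, about 4, so about 9 patients.

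**2. Counting the MPO tests.**

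| Source | MPO rows | Printed p |
|---|---|---|
| Table 13 | post-op, pre-op, post-op × technique, pre-op × technique | 0.3, 0.5, 0.3, 0.9 |
| Table 16 | post-op, pre-op | 0.2, 0.04 |
| Table 19 | post-op, pre-op | 0.8, 0.1 |

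That is eight, of which one is below 0.05. The pump-assisted model fits two more MPO terms without printing them.

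**3. Adjusting the smallest p (number of tests × p; for the smallest p, Holm gives the same).**

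| Family | From 0.04 | From 0.044 |
|---|---|---|
| Three printed pre-operative main-effect rows | 0.12 | 0.13 |
| Six printed main-effect rows | 0.24 | 0.27 |
| All eight printed MPO rows | 0.32 | 0.36 |
| Ten, with the two unprinted pump-assisted terms | 0.40 | 0.44 |

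None is below 0.05. If all eight nulls held, the chance of at least one p<0.05 would be 1 − 0.95⁸ = 0.34 under independence. The tests overlap, so this is an upper guide: simulation with assumed correlations of 0.5 and 0.9 gives 0.25 and 0.12.

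**4. What the interaction test does and does not say.** The tables give no slopes or signs. Taking √4.2 = 2.05 on-pump and √2.36 = 1.54 off-pump as approximate z values:

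- If the signs agree, (2.05 + 1.54)/√2 = 2.54, p about 0.011 for a common slope. With assumed variance ratios from 0.5 to 4 the range is 0.010 to 0.015.
- If the signs are opposite, the on-versus-off difference would have p of about 0.010 to 0.022 over the same ratios, which fits poorly with the printed 0.9.

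So p=0.9 is compatible with a common non-zero slope. The all-patient main effect (p=0.5) does not settle the matter. It is fitted beside its own interaction, where a Type III test usually refers to the unweighted average slope over the three groups. The pump-assisted group, with about 9 patients, would then dominate its error.

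**The case against.** The strongest defence is that the study is declared exploratory, pre-operative MPO is named in the on-pump hypothesis, and the Table 1 conclusion is tentatively worded. All of that stands. Absence of adjustment is not in itself a breach, and the choice of family is the reviewer's: the adjusted p is 0.12 or 0.32 depending on it. But an exploratory label calls for exploratory wording, and the on-pump Summary does not use it. The MPO hypothesis was also named in all four TnI sections, for pre- and post-operative values alike, so it is one of a set.

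Three stronger readings are tempting, and the documents do not support them.

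- *The plan claims an on-pump-only effect, and its own interaction test refutes it.* The on-pump Summary makes no comparison with the other techniques. An interaction p of 0.9 does not contradict p=0.04 within one group.
- *Pre-operative MPO is unrelated to TnI.* The all-patient p=0.5 and the pump-assisted null are weak evidence, and the on- and off-pump results may point the same way.
- *Within Table 16, only bypass time survives correction.* Bonferroni over the eight rows gives 8 × 0.006 = 0.048 for CPBTime (0.044 to 0.051 allowing for rounding) and 8 × 0.02 = 0.16 for AoClamp*CPBTime. But CPBTime is fitted beside interactions that contain it. No centring is described; without it, that row is a slope at zero clamp and operation time. Keeping it while discarding its interaction would not be sound.

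**Conclusion.** The concern holds as a matter of interpretation. The on-pump Summary presents as an effect a nominal association with p=0.044, the only one of eight printed MPO–TnI tests below 0.05. It stays above 0.05 under every family considered, from 0.12 for the narrowest to 0.44 for the widest. There is no evidence that the pre-operative MPO slope differs by technique, so the technique summaries should not be read as a contrast. Whether a common slope exists is open.

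Assumptions: a two-sided 0.05 level, which the document does not state; error df recovered from rounded table entries; and, for the combined on- and off-pump figure only, agreeing signs and the stated variance ratios. Here unadjusted means unadjusted for multiplicity; the models do adjust for covariates. The on-pump model also uses only about 74 of 128 patients, which limits the result further.

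**What to change.** 1. In the on-pump, off-pump and pump-assisted TnI sections, label the models hypothesis-generating and unadjusted for multiplicity.
2. In the on-pump Summary, describe day-1 TnI as *nominally associated with* pre-operative MPO (p=0.04, unadjusted for multiplicity) in place of the present verb.
3. Refit the all-patient model without the MPO-by-CPBTYPE terms and report one common pre-operative MPO slope with its 95% CI.
4. Have the Table 1 conclusion on myocardial damage rest on that estimate, stated as a hypothesis.

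A formal multiplicity procedure is not required in an exploratory study, and technique-specific statements need not wait for a significant interaction: with so few pump-assisted patients, that test would be a poor filter.

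Cost: wording changes and one refit on existing data. The on-pump statement is softened. The common-slope estimate may weaken or strengthen the case for MPO.

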#### **Ischemic – reperfusion injury analysis (TnI level 1st day after off – pump CABG)**

Hypothesis: TnI level 1st day after off-pump CABG depends on length of operation, MPO level before procedure and after suture performing

Method of hypothesis testing: ANCOVA

ANCOVA model: LGTnI1= LGMPOPostOp LGMPOPreOp OpTime

*Table 17 Variables description*

Variable	Description	Note
TnI1	Troponin I level 1 st day after procedure	Continuous variable
LGMPOPostOp	Logarithm of MPO level during CABG (after suture performing)	Log – transformation for normal distribution
LGMPOPreOp	Logarithm of MPO level before CABG (after suture performing)	Log – transformation for normal distribution
OpTime	Length of procedure, min	Continuous variable

*Table 18 Characteristics of model*

Source	Sum of Squares	df	Mean Square	F	p	Eta Square
Model	43.7	3	14.6	7.0	0.0002	0.15

Assessment of Myocardial Ischemic-Reperfusion Injury During Off- and On- Pump CABG (ClinicalTrials.gov Identifier: NCT03050489). Corresponding author: [name] [[contact]](mailto:[contact]) [contact]

Date of the document 06 December 2016

*Table 19 Characteristics of model LGTnI1= LGMPOPostOp LGMPOPreOp OpTime*

Source	Sum of Squares (Type III)	df	Mean Square	F	p	Partial Eta Squared
LGMPOPostOp	0.1	1	0.1	0.06	0.8	0.0005
LGMPOPreOp	4.9	1	4.9	2.36	0.1	0.02
OpTime	38.5	1	38.5	18.58	0.0001	0.1

Summary: troponin I level 1st day after on-pump CABG affected by length of operation.

#### **Ischemic – reperfusion injury analysis (TnI level 1st day after pump – assisted CABG)**

Hypothesis: TnI level 1st day after pump – assisted CABG depends on length of operation, MPO level before procedure and after suture performing and cardiopulmonary bypass.

Method of hypothesis testing: ANCOVA

ANCOVA model: LGTnI1= LGMPOPostOp LGMPOPreOp OpTime CPBType

*Table 20 Variables description*

Variable	Description	Note
TnI1	Troponin I level 1 st day after procedure	Continuous variable
LGMPOPostOp	Logarithm of MPO level during CABG (after suture performing)	Log – transformation for normal distribution
LGMPOPreOp	Logarithm of MPO level before CABG (after suture performing)	Log – transformation for normal distribution
OpTime	Length of procedure, min	Continuous variable
CPBType	Group of intervention	1 – off-pump CABG 2 – on – pump CABG 3 – pump-assisted CABG

*Table 21 Characteristics of model*

Source	Sum of Squares	df	Mean Square	F	p	Eta Square
Model	3.7	4	0.9	0.8	0.6	0.45

**Summary:** TnI level 1st day after pump – assisted CABG does not depend on MPO level and length of cardiopulmonary bypass grafting.

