### Primary endpoint analysis

Hypothesis: MPO levels after procedure are different between groups.

Hypothesis testing:

- Normality test (Kolmogorov-Smirnov test, Shapiro-Wilk test)

Group comparing:

Continuous variables

- Non-normal distribution: Kruskal-Wallis test with adjustment for multiple comparisons

*Table 6 Myeloperoxidase variables specifications*

Characteristic	Variable name in database	Test
MPO level before procedure	MPOPreOp	Kruskal-Wallis test
MPO level after procedure	MPOPostOp	Kruskal-Wallis test

*Table 7 Myeloperoxidase before and during coronary artery bypass grafting (CABG)*

Variables	off-pump CABG (N=181)	on-pump CABG (N=128)	pump-assisted CABG (N=27)	P Value*
MPO before CABG				0.2904
Nmiss (%)	34 (18.8)	21 (16.4)	9 (33.3)	
Mean±SD	35.8±32.1	39.9±30.6	29.2±14.8	
Min–Max	2.8–237.8	4.0–168.9	5.6–65.4	
Median (IQR)	27.7 (17.0–41.0)	31.0 (19.0–48.7)	29.0 (18.7–34.0)	
MPO after CABG				<.0001
Nmiss (%)	28 (15.5)	26 (20.3)	13 (48.1)	

Date of the document 06 December 2016

Variables	off-pump CABG (N=181)	on-pump CABG (N=128)	pump-assisted CABG (N=27)	P Value*
Mean±SD	96.2±75.3	210.9±138.7	175.0±102.6	
Min–Max	9.1–410.3	16.7–824.6	63.4–374.5	
Median (IQR)	66.5 (41.3–135.8)	184.3 (135.0–250.0)	144.7 (95.0–284.9)	

\* Kruskal-Wallis test, Nmiss – number of missing values, SD – standard deviation, IQR – interquartile range, CABG – coronary artery bypass grafting

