### **Missing data analysis**

*Table 25 Missing data analysis*

MPOPostOp	off-pump CABG (N=181)	on-pump CABG (N=128)	pump-assisted CABG (N=27)
Present	153 (84.5)	102 (79.7)	14 (51.9)
Missing	28 (15.5)	26 (20.3)	13 (48.1)

CABG – coronary artery bypass grafting.

Reason of missingness: laboratory test shows exceeding upper scale limit. Results could be biased.

Hypothesis: postoperative MPO level too high to determine with current assay.

Hypothesis testing: new clinical trial with larger number of patients could this hypothesis tested.

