Reoperation non cardio				0.07 40**
No	177 (97.8)	119 (93.0)	27 (100)	
Yes	4 (2.2)	9 (7.0)		
Kidney Damage				<.00 01**
Cr< URL	130 (71.8)	52 (40.6)	17 (63.0)	
Cr> 25% URL	49 (27.1)	70 (54.7)	7 (25.9)	
Hemodialysis				
2 (1.1)	6 (4.7)	3 (11.1)		
Atrial fibrillation				0.07 84**
No	155 (85.6)	101 (78.9)	19 (70.4)	
Yes	26 (14.4)	27 (21.1)	8 (29.6)	
Multiorgan dysfunction after CABG				0.00 17**
No	179 (98.9)	116 (90.6)	25 (92.6)	
Yes	2 (1.1)	12 (9.4)	2 (7.4)	
Infection or leukocytosis or febril >7 days				0.86 34**
No	166 (91.7)	117 (91.4)	26 (96.3)	
Yes	15 (8.3)	11 (8.6)	1 (3.7)	
Bleeding after CABG				0.00 14**
No	178 (98.3)	114 (89.1)	26 (96.3)	
Yes	3 (1.7)	14 (10.9)	1 (3.7)	
Graft thrombosis within 30d after CABG				0.82 95**
No	175 (96.7)	122 (95.3)	26 (96.3)	

Variables	off-pump CABG (N=181)	on-pump CABG (N=128)	pump-assisted CABG (N=27)	P Value
Yes	6 (3.3)	6 (4.7)	1 (3.7)	
Pulmonary dysfunction after CABG				0.04 92**
No	171 (94.5)	117 (91.4)	21 (80.8)	
Yes	10 (5.5)	11 (8.6)	5 (19.2)	
Neurological complications within 30d after CABG				0.03 22**
No	175 (96.7)	124 (96.9)	23 (85.2)	
Yes	6 (3.3)	3 (2.3)	3 (11.1)	
Death within 30d after CABG				0.25 45**
No	177 (97.8)	121 (94.5)	27 (100)	
Yes	4 (2.2)	7 (5.5)		
Intestinal complications within 30d after CABG				0.27 73**
No	180 (99.4)	127 (99.2)	26 (96.3)	
Yes	1 (0.6)	1 (0.8)	1 (3.7)	

\* Kruskal-Wallis test, \*\* exact Fisher's test. Nmiss – number of missing values, SD – standard deviation, IQR – interquartile range, CABG – coronary artery bypass grafting

Table 30 Troponin I level after CABG

Variables	off-pump CABG (N=181)	on-pump CABG (N=128)	pump-assisted CABG (N=27)	P Value
TnI before CABG				0.0938
Nmiss (%)	145 (80.1)	99 (77.3)	19 (70.4)	
Mean±SD	0.0±0.1	0.0±0.1	0.0±0.0	
Min–Max	0.0–0.5	0.0–0.2	0.0–0.1	
Median (IQR)	0.0 (0.0–0.0)	0.0 (0.0–0.0)	0.0 (0.0–0.1)	
TnI 1st day				<.0001
Nmiss (%)	17 (9.4)	10 (7.8)	1 (3.7)	
Mean±SD	2.5±8.9	6.0±10.3	4.7±7.3	
Min–Max	0.0–98.0	0.0–93.0	0.3–31.1	
Median (IQR)	0.4 (0.2–1.0)	3.1 (1.8–6.3)	1.4 (0.7–6.8)	
TnI 2st day				<.0001
Nmiss (%)	104 (57.5)	39 (30.5)	9 (33.3)	
Mean±SD	3.5±8.2	3.9±7.9	4.5±5.9	

Date of the document 06 December 2016

Variables	off-pump CABG (N=181)	on-pump CABG (N=128)	pump-assisted CABG (N=27)	P Value
Min–Max	0.0–50.0	0.0–50.0	0.2–18.8	
Median (IQR)	0.4 (0.2–2.1)	1.5 (0.7–3.4)	0.9 (0.4–6.1)	
TnI 3st day				0.1936

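### The pump-assisted troponin model is not the one its table and summary describe, and its result is inconclusive rather than evidence of no dependence

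*Combined protocol and SAP*

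**What the plan says.** All references are to the combined protocol and SAP. The section on day-1 troponin I after pump-assisted CABG gives the model as "LGTnI1= LGMPOPostOp LGMPOPreOp OpTime CPBType". Table 20 describes CPBType as the group of intervention, coded "1 – off-pump CABG 2 – on – pump CABG 3 – pump-assisted CABG". The section's hypothesis names as predictors the length of operation, "MPO level before procedure and after suture performing and cardiopulmonary bypass".

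Table 21 has a single row, "Model 3.7 4 0.9 0.8 0.6 0.45", under the columns sum of squares, df, mean square, F, p and eta squared. No error df, no number of patients and no per-predictor table follow. The on-pump and off-pump sections do give per-predictor results (Tables 16 and 19). The summary states that troponin I in this group "does not depend on MPO level and length of cardiopulmonary bypass grafting".

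The synopsis (Table 2) says that observations with missing data are dropped. Table 25 shows postoperative MPO present in 14 of the 27 pump-assisted patients ("Present 153 (84.5) 102 (79.7) 14 (51.9", last column).

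**The concern.** Three things do not fit together. A grouping variable cannot be estimated inside one of its own groups, so the written formula cannot give the printed df. The summary concludes on a variable, length of bypass, that the written model does not contain. The on-pump section defines CPBTime separately from CPBTYPE, so these are two different variables. And a non-significant overall test is reported as a positive finding of no dependence, with no n or interval by which a reader could judge it.

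This is the only troponin model for the pump-assisted group on its own, and troponin I stands under the primary objective. A reader would take away a negative scientific statement about one of the three techniques that cannot be traced to a specified analysis.

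**Working it through.** **Step 1. Count the model df.** LGMPOPostOp, LGMPOPreOp and OpTime are continuous, with 1 df each. CPBType is always 3 in this group and adds 0 df. The total is 3, against 4 printed.

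The on-pump section supports this count. Its formula also lists CPBTYPE and an LGMPOPreOp by CPBTYPE interaction. Its printed model df is 8 (Table 15), which equals the eight other terms listed in Table 16, so the constant terms contributed nothing there.

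**Step 2. See which df the printed row fits.** Mean square = sum of squares / df.
- With 4 df: 3.7/4 = 0.925, which agrees with the printed 0.9.
- With 3 df: 3.7/3 = 1.23, which does not.

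Replacing CPBType by the continuous CPBTime gives 4 df. It also matches the hypothesis and the summary, both of which refer to bypass.

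**Step 3. Back-calculate the error df.** Error df = F × model df × (1 − eta²)/eta².
- 0.8 × 4 × 0.55/0.45 = 3.91.
- With F between 0.75 and 0.85 and eta² between 0.445 and 0.455 (rounding), the range is 3.59 to 4.24, so 4.
- n = 4 + 4 + 1 = 9.
- The p-value for F(4,4) = 0.8 is 0.58, against 0.6 printed. This is only weak confirmation, because p changes little with error df (0.60 at 3, 0.57 at 5).

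**Step 4. Check that this n is possible.** Among the 27 pump-assisted patients:
- postoperative MPO is present in 14 (Table 25);
- preoperative MPO is missing in 9 (Table 7, "34 (18.8) 21 (16.4) 9 (33.3"), so present in 18;
- day-1 troponin I is missing in 1 (Table 30, "17 (9.4) 10 (7.8) 1 (3.7"), so present in 26.

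Patients with all three number at least 14 + 18 + 26 − 2 × 27 = 4 and at most 14. Nine lies in that range.

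**Step 5. What such a model can show (5% level assumed).** With 4 and 4 df the critical F is 6.39. The R² needed is 6.39 × 4/(6.39 × 4 + 4) = 0.86. At the ceiling of 14 patients (4 and 9 df) the critical F is 3.63 and the R² needed is 3.63 × 4/(3.63 × 4 + 9) = 0.62.

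**Step 6. What 0.45 means at this size.** With no association at all, the expected R² is model df/(n − 1) = 4/8 = 0.50. Adjusted R² = 1 − 0.55 × 8/4 = −0.10. The observed value is about what chance produces.

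**The case against.** The strongest reply is that CPBType is a slip for CPBTime. The fitted model then held no constant, and its estimates are unaffected. A truly constant term would change no estimate either. This is probably right, and a reader should not infer that the fit itself is invalid. But the slip stands in both the formula and Table 20, so the text needs correcting, and the explanation does nothing for the claim of no dependence. Another route to 4 df would be the 33 patients who actually had pump-assisted surgery, with CPBType holding the planned group. The documents describe no such analysis, and the group tables use 27.

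Second, n = 9 is inferred from one rounded row, in a document whose other ANCOVA tables contain slips (Table 10 pairs F = 0.2 with p = 0.0001; Table 13 pairs sum of squares 2.0 on 1 df with mean square 2.6). That is fair. The number should be requested from the data and not written into the plan from this calculation.

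Third, the study is labelled exploratory and has no sample size calculation. The missing-data section itself warns of possible bias, the synopsis conclusions do not repeat this negative statement, and the primary MPO comparison is untouched. All of this limits the reach of the point. An exploratory label excuses low power, but not a categorical negative conclusion.

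A reader might also infer a strong missed association, because 0.45 exceeds the eta squared of the on-pump model (0.4) and the off-pump model (0.15). The documents do not support this. Raw eta squared is not comparable across models of such different size. By the formula in step 3, error df is 5.4 × 8 × 0.6/0.4 = 64.8 on-pump and 7.0 × 3 × 0.85/0.15 = 119 off-pump. Adjusted R² is then 1 − 0.6 × 72.8/64.8 = 0.33 and 1 − 0.85 × 122/119 = 0.13, against −0.10 here. Nor does a power figure computed at the observed R² help, since it only restates the p-value.

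**Conclusion.** The point holds. The written formula gives 3 model df against 4 printed, and the summary rests on a covariate that is in neither the formula nor Table 20. The claim of no dependence is unsupported: on the printed figures the model had about 4 error df and could have reached significance only with R² above about 0.86. The data are equally far from showing dependence, so the right word is inconclusive.

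The df mismatch follows directly from the text. The size of the problem rests on Table 21's F and eta squared being correctly printed, on 4 model df, and on a 5% level. That CPBTime was the covariate fitted is the likeliest explanation, but it is not documented. This is a local correction that should be made; it does not touch the primary endpoint comparison.

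**What to change.** - In the formula and in Table 20, replace CPBType with the covariate actually fitted. If that was not CPBTime, remove the statement on length of bypass from the summary.
- Remove the CPBTYPE term and its interaction from the on-pump formula, where they are constant too. The printed 8 df already exclude them, so no result should change.
- Report the actual complete-case n, the error df, and each predictor's slope with its 95% confidence interval for the pump-assisted model.
- Replace the claim of no dependence with a statement that the result is inconclusive because too few patients have complete data.

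The cost is one rerun of a small model and a few lines of text. The scientific cost is that a negative claim becomes an inconclusive one.
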